## 7 STUDY INTERVENTION DISCONTINUATION AND PARTICIPANT DISCONTINUATION/WITHDRAWAL

### 7.1 EARLY DISCONTINUATION OF SUBJECTS

Each subject reserves the right to withdraw from the study at any time without jeopardy to her future medical care. All follow-up assessments and procedures

should be performed at the final study visit. For any subject who discontinues from the study, the date and reason for discontinuation will be recorded.

If a subject fails to return for one or more scheduled study visits, the Investigator will attempt to contact the subject to determine and document the reason the subject has failed to return and to encourage compliance with the study visit schedule.

A subject may be discontinued from the study for the following reasons:

- Subject did not undergo arthroscopic debridement as it was deemed not warranted by the Investigator
- Since enrollment in the study, subject has had alternative treatment that would otherwise affect the study questionnaire/outcomes data
- Subject does not complete scheduled follow-up visits per protocol
- Subject has died

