## 9 STATISTICAL PROCEDURES

Every attempt will be made to collect complete data and limit the occurrence of missing data. Due to the descriptive nature of all analyses, no imputation of missing data will be performed. Descriptive summaries will be based on all observations available within each of the relevant analysis populations.

Descriptive statistics will be presented for key outcome measures.

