### 9.1 POPULATIONS FOR ANALYSES

All subjects will be included in the full analysis population. The per protocol population is defined as subjects who have not had any major protocol deviations throughout the study (Section 9.8) and will be analyzed as the primary study group. Other subgroups may be analyzed as detailed in the subgroup analyses section. Subjects that have been discontinued will be excluded from data analysis.

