### 9.3.4 SAFETY ANALYSIS

Safety analyses will include the incidence and severity of adverse events observed over the study assessment period. These will be tabulated and presented overall and by relatedness, severity, and preferred term.

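### Section 9.1 excludes discontinued subjects from analysis without exempting safety and contradicts its own full analysis population, so the adverse event tables can lose treated subjects and their events

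*Combined protocol and SAP*

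**What the plan says.** Section 9.1 is the only place that defines analysis populations. It opens with "All subjects will be included in the full analysis population", then defines a per protocol population as the primary study group, and closes with "Subjects that have been discontinued will be excluded from data analysis". The closing sentence is not limited to efficacy. No safety or as-treated population appears anywhere in the document.

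Section 9.3.4 plans AE incidence and severity over the assessment period. On layout it says: "These will be tabulated and presented overall and by relatedness, severity, and preferred term". It names neither a population nor a denominator. The introduction to section 9 says: "Descriptive summaries will be based on all observations available within each of the relevant analysis populations".

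Section 7.1 lets a subject withdraw at any time and then gives a permissive list, introduced by "A subject may be discontinued from the study for the following reasons". The list has four reasons: no debridement, alternative treatment, incomplete follow-up, and death.

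**The concern.** An AE table should account for everyone exposed to the study procedures, including those who leave early, because leaving may be connected with an event. Here the only rule on discontinued subjects removes them from analysis, and nothing brings them back for safety. An analyst applying 9.1 as written could drop an injected subject and that subject's events from both numerator and denominator. Death is the plainest case: section 11.1.2 counts it as an SAE and section 7.1 lists it as a reason for discontinuation.

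What is at stake is the planned safety summary of a 48-subject trial, where one or two exclusions visibly change a reported rate.

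**Working it through.** **Step 1: the sentences of 9.1 side by side.** Take a subject who is injected and discontinued at month 3. By "All subjects will be included in the full analysis population" that subject is in the full analysis population. By "Subjects that have been discontinued will be excluded from data analysis" the subject is out of analysis. The two give different AE denominators.

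**Step 2: does another section settle it?** Section 9.3.4 names no population. The introduction to section 9 refers summaries to the relevant populations, which leads back to 9.1. The conflict remains.

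**Step 3: can a treated subject be discontinued?** Under section 6.3, randomisation follows debridement; PRP subjects then have about 9 cc of blood drawn, and the injection comes after that. Against this sequence, the routes in 7.1 are:

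| Route | Can it follow the injection? |
|---|---|
| "Subject did not undergo arthroscopic debridement as it was deemed not warranted by the Investigator" | No; it precedes randomisation, so no exposed subject is lost |
| "subject has had alternative treatment that would otherwise affect the study questionnaire/outcomes data" | Yes |
| "Subject does not complete scheduled follow-up visits per protocol" | Yes |
| Death | Yes |
| Voluntary withdrawal at any time | Yes, including directly after a complication |

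Three of the four listed reasons, and withdrawal, can therefore remove an injected subject. None of the listed reasons other than death is itself an adverse event.

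**Step 4: effect on the table.** The only input from the documents is N = 48 (section 5.1, 24 + 24). That figure is not in dispute: with the inputs of section 9.6 (difference 15, SD 18, two-sided 5%, power 80%), a two-sample t-test needs 23.6 per arm, rounded up to 24. All other counts below are assumptions, because the documents give no AE, death or discontinuation rate.

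Let E be the number of subjects with an event, d the number discontinued after injection, and k the number of those d with an event.

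- Full incidence: E/N.
- Tabulated incidence under the exclusion: (E − k)/(N − d).
- The count of subjects with events falls by k.
- The percentage falls when (E − k)N < E(N − d), that is, when k/d > E/N. It is unchanged when k/d = E/N and rises when k/d < E/N.

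| E | d | k | k/d | Full | Tabulated |
|---|---|---|---|---|---|
| 1 (a death) | 1 | 1 | 100% | 1/48 = 2.1% | 0/47 = 0% |
| 4 | 1 | 1 | 100% | 4/48 = 8.3% | 3/47 = 6.4% |
| 4 | 2 | 2 | 100% | 8.3% | 2/46 = 4.3% |
| 4 | 3 | 3 | 100% | 8.3% | 1/45 = 2.2% |
| 4 | 4 | 4 | 100% | 8.3% | 0/44 = 0% |
| 4 | 6 | 2 | 33.3% | 8.3% | 2/42 = 4.8% |
| 4 | 6 | 1 | 16.7% | 8.3% | 3/42 = 7.1% |
| 4 | 6 | 0 | 0% | 8.3% | 4/42 = 9.5% |
| 4 | 13 | 1 | 7.7% | 8.3% | 3/35 = 8.6% |

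The last row shows that an event can be lost while the percentage rises. Equal rates in those discontinued and those retained preserve only the overall percentage. The counts, and the breakdowns by severity and preferred term, can still change.

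**The case against.** The best defence is that the exclusion was meant for efficacy only. Section 9.3.4 describes its scope by events observed, without a population limit. The reference to relevant populations in section 9 is followed by a sentence about key outcome measures, so it may be aimed at outcomes. The full analysis population could serve for safety. This reading is possible, but the text does not state it, and the exclusion sentence covers data analysis without limit.

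A second defence is that safeguards exist. AEs are asked about at all visits (8.2), recorded on a case report form (11) and reported to the IRB (11.2); SAEs are to be reported within 24 hours (11.3). All of that stands, and it limits the consequence. These are collection and reporting rules, however, and none puts a discontinued subject into the 9.3.4 tables.

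A third is that the discontinuation list is permissive and no rates are given. That also stands: exclusion is possible rather than certain, and its size cannot be derived.

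A reader might go further and infer that the plan sets out to discard adverse events, that safety data will be lost, or that reported incidence must be too low. The documents support none of these. The conflict in 9.1 leaves the intention open, the records survive, and the direction of the percentage depends on who is discontinued.

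**Conclusion.** The point holds as a contradiction in 9.1 that, read literally, can remove treated subjects and their events from the AE tables. The counts are understated whenever an excluded subject had an event. The incidence percentage is understated only if subjects with events are over-represented among those discontinued (k/d > E/N).

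The size is illustrative only: on assumed counts, 1/48 becomes 0/47 for a single excluded death, and 4/48 (8.3%) becomes anything from 0% to 9.5% in the cases shown. The conclusion rests on the literal reading of the exclusion sentence and on at least one subject being discontinued or withdrawing after a study procedure has begun. The plan should be corrected before analysis, because it supports two different safety denominators. The source data are not at risk.

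**What to change.** In section 9.1:

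- State that the exclusion of discontinued subjects does not apply to safety, and reconcile that sentence with the one placing all subjects in the full analysis population.
- Define a safety population: all randomised subjects in whom any study procedure was begun (the PRP blood draw, or injection of PRP or saline), analysed by injection received, or by assigned arm if none was given. Include those later discontinued, withdrawn or dead. Starting from the first study procedure matters because a set limited to injected subjects would miss an event at the blood draw.

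In section 9.3.4, name this population as the basis for the AE and SAE tables. Showing the tables by arm with denominators, as well as overall, is an optional clarification; the present text does not forbid it.

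The cost is wording in two sections and slightly more tabulation. No new data or visits are needed, because AEs and the date and reason for discontinuation are already to be recorded.

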### 9.2 COLLECTION AND DERIVATION OF PRIMARY AND SECONDARY OUTCOME MEASURES

### 9.2.1 PRIMARY OUTCOME MEASURES

The primary outcome measure is the difference in improvement between preoperative and post-operative pain scale scores, grip strength, wrist range of motion, Patient-rated Wrist Evaluation (PRWE) scores, and Modified Mayo Wrist scores between patients treated with PRP and patients not treated with PRP after arthroscopic debridement.

### 9.2.2 SECONDARY OUTCOME MEASURES

Not applicable

### 9.2.3 EXPLORATORY MEASURES

All exploratory variables will be analyzed as reported, without further derivation, except for the calculation of change from baseline, or change from prior time-points.

## 9.3 HYPOTHESIS AND METHODS OF ANALYSIS

We hypothesize that use of PRP after arthroscopic debridement will result in greater pain reduction and improved functional outcomes when compared to arthroscopic debridement alone, as measured by pain scale scores, grip strength, wrist range of motion, Patient-rated Wrist Evaluation (PRWE) scores, and the Modified Mayo Wrist Score.

### 9.3.1 PRIMARY OUTCOME MEASURE ANALYSIS

The primary outcome measure is the difference in improvement between preoperative and post-operative pain scale scores, grip strength, wrist range of motion, Patient-rated Wrist Evaluation (PRWE) scores, and Modified Mayo Wrist scores between patients treated with PRP and patients not treated with PRP after arthroscopic debridement.

Preoperative and postoperative outcome measures will be analyzed using descriptive statistics, including n, mean, standard deviation, median, minimum, maximum, and skewness.

### 9.3.2 SECONDARY OUTCOME MEASURE ANALYSIS

Not applicable.

### 9.3.3 EXPLORATORY MEASURES ANALYSIS

All exploratory variables will be summarized with descriptive statistics appropriate to the scale of measurement for each variable.

### 9.3.4 SAFETY ANALYSIS

Safety analyses will include the incidence and severity of adverse events observed over the study assessment period. These will be tabulated and presented overall and by relatedness, severity, and preferred term.

## 9.4 SUBGROUP ANALYSIS

Subgroup analyses will be performed to explore their relationship to key study outcomes.

## 9.5 EXPLORATORY ANALYSES

The difference in preoperative versus postoperative outcomes within groups (treatment versus placebo) will be tested for significance using paired t-tests. The significance of differences in preoperative versus postoperative outcomes between groups (treatment and placebo group) will be analyzed using 2-sample t-tests. Additional analyses of possible relationships between outcomes may also be performed using appropriate inferential tests.

## 9.6 SAMPLE SIZE CALCULATION

The trial will be powered to detect a difference in post-treatment PRWE scores between groups of 15, deemed to be clinically significant by the investigators. The standard deviations for PRWE scores previously published after treatment for TFCC tears ranges from 6.6 to 20.5. To detect a mean difference in post-treatment PRWE score of 15 points ( $SD = 18$ ) with a two-sided significance level of 5% and power of 80% with equal allocation to two arms would require 24 patients in each arm of the trial.

Subjects will be assessed per standard of care of their clinical requirement and qualification for surgery and upon subject's decision to participate in the study. The difference in preoperative and postoperative outcomes will be analyzed to

determine which group has the most improvement based on the following outcomes: pain scale scores, wrist range of motion, PRWE scores, and Modified Mayo Wrist scores.

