### 6.1.2 PRE-OPERATIVE VISITS

The subject will be screened in accordance with the inclusion/exclusion criteria and medical history collected. Pre-operative visual pain analogue score measurements, grip strength and wrist range of motion measurements, and Patient-rated Wrist Evaluation (PRWE) scores and Modified Mayo Wrist scores will be collected. Subject health information (e.g., demographics, general health), physical examination, medical photography, and hand imaging (see section 6.2) will be performed at screening.

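### The 80% power in section 9.6 is for post-treatment PRWE with all 24 per arm analysed; power for the unadjusted t-test on change named in 9.5 is not established

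*Combined protocol and SAP*

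**What the plan says.** Section 9.6 sizes the trial on the post-operative score. Its target is worded "To detect a mean difference in post-treatment PRWE score of 15 points", and the spread it assumes for that score is an SD of 18. From these inputs the section concludes that the comparison "with a two-sided significance level of 5% and power of 80% with equal allocation to two arms would require 24 patients in each arm". It gives the source range for the SD: "The standard deviations for PRWE scores previously published after treatment for TFCC tears ranges from 6.6 to 20.5". Section 5.1 randomises exactly that number, 24 to PRP and 24 to saline.

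The outcome to be compared is different. Sections 8.1.1, 9.2.1 and 9.3.1 define the primary outcome as the between-arm difference in improvement from before to after surgery, and 9.3.1 analyses it descriptively. The only between-group test named is in 9.5, under exploratory analyses: "The significance of differences in preoperative versus postoperative outcomes between groups (treatment and placebo group) will be analyzed using 2-sample t-tests". No covariate is mentioned, although 6.1.2 collects the baseline on every subject: "Pre-operative visual pain analogue score measurements, grip strength and wrist range of motion measurements, and Patient-rated Wrist Evaluation (PRWE) scores".

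Three provisions bear on how many subjects are analysed. Section 7.1 lists as a possible reason for discontinuation: "Subject does not complete scheduled follow-up visits per protocol". Section 9.1 says: "Subjects that have been discontinued will be excluded from data analysis". Section 9 adds: "Due to the descriptive nature of all analyses, no imputation of missing data will be performed". Section 9.1 also makes the per-protocol set the primary study group, which removes subjects with major deviations. No expected loss is stated.

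**The concern.** A power statement describes one test, on one variable, in a given number of analysed subjects. Here the variable used for sizing (post-operative score) is not the variable tested (change), and the number sized for (24) is the number randomised, not the number expected in the analysis.

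The variance of a change score can be smaller or larger than that of the post-operative score, depending on two quantities that the documents do not give. A reader of 9.6 therefore cannot tell what power the between-group comparison has. Under randomisation the change-score t-test is unbiased, so what is at stake is precision. In a 48-subject trial the choice of analysis matters a good deal, and a baseline measurement that could improve precision goes unused as a covariate.

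**Working it through.** **Inputs from the documents (9.6, 5.1):** difference 15, post-operative SD 18, two-sided 5%, 24 per arm, published SD range 6.6 to 20.5.

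**Assumptions, because the documents are silent:** pre/post correlation r from 0.3 to 0.8; pre-operative SD 12, 18 or 22; 20 analysed per arm as an illustration of loss.

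**Step 1. Reproduce the plan's figure.** Noncentrality = 15 / (18 × √(2/24)) = 2.887 on 46 degrees of freedom. Noncentral-t power is 80.7%, so 24 per arm is right. With fewer analysed, power is 78.9% (23 per arm), 77.0% (22) and 72.8% (20). At SD 18 there is no margin.

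**Step 2. Power of the change-score t-test.** SD of change = √(SDpre² + SDpost² − 2·r·SDpre·SDpost). With both SDs 18 this is 18 × √(2(1−r)).

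**Step 3. Power of ANCOVA on the post-operative score.** Residual SD = 18 × √(1−r²), degrees of freedom 2n−3, variance multiplied by 1 + 1/(2n−4) for estimating the slope. A simulation with 40,000 trials per setting agreed within 0.3 points at 24 per arm.

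| r | SD of change | Change score, 24 per arm | ANCOVA, 24 per arm | Change score, 20 per arm | ANCOVA, 20 per arm |
|---|---|---|---|---|---|
| 0.3 | 21.3 | 66.6% | 83.3% | 58.3% | 75.6% |
| 0.4 | 19.7 | 73.2% | 86.2% | 65.0% | 78.9% |
| 0.5 | 18.0 | 80.7% | 89.7% | 72.8% | 83.2% |
| 0.6 | 16.1 | 88.5% | 93.7% | 81.9% | 88.6% |
| 0.7 | 13.9 | 95.4% | 97.4% | 91.2% | 94.3% |
| 0.8 | 11.4 | 99.4% | 99.6% | 98.2% | 98.8% |

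**Step 4. Where the change score breaks even with 9.6.** Setting the SD of change equal to SDpost gives r = SDpre / (2 × SDpost): 12/36 = 0.33, 18/36 = 0.50 and 22/36 = 0.61 for pre-operative SDs of 12, 18 and 22. Below that r, the change-score test has less power than 9.6 states; above it, more.

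**Step 5. Effect of the pre-operative SD (24 per arm, post-operative SD 18).** At r = 0.3, change-score power is 79.0% with SDpre 12 and 56.8% with SDpre 22. At r = 0.5 it is 89.3% and 70.8%. ANCOVA power does not depend on SDpre.

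**Step 6. Effect of the post-operative SD (post-treatment t-test, 24 and 20 per arm).** SD 13.55, the midpoint of the cited range: 96.4% and 92.7%. SD 16: 88.9% and 82.4%. SD 20.5, the top of the range: 69.9% and 61.6%, with 31 per arm needed for 80%.

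**The case against.** The strongest reply is that nothing in 9.6 is miscalculated and no shortfall has been shown. The change-score test may have more power than stated, and the spread in the table comes from assumed correlations and SDs. That is true, and it is why the conclusion is that power is not established rather than that it is too low. Only the effect of losing subjects has a fixed direction at a given SD.

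Second, the plan calls itself descriptive: the synopsis says 48 subjects suffice for descriptive summaries and exploratory analyses, 9.3.1 is descriptive, and the t-tests are exploratory. This lowers the weight of the point. It does not remove it, because 9.6 says the trial is powered to detect a difference, 9.3 states a directional hypothesis, and the 9.5 test is the only one named that could address it.

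Third, SD 18 already lies high in the cited range. At the midpoint of 13.55, with equal SDs before and after, even the change score at r = 0.3 has 88.7% with 24 per arm and 82.2% with 20. That stands; equally, the top of the range is worse than planned.

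Fourth, ANCOVA cures neither loss nor a larger SD. With 20 per arm it gives 71.6% at r = 0 and 75.6% at r = 0.3; at SD 20.5 with 24 per arm it gives 68.9% and 72.9%. This also stands, and is why 9.6 needs rewording as well as 9.5.

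Finally, 9.5 could be read as a t-test on post-operative scores, which would match 9.6. Sections 4.3, 8.1.1 and 9.2.3 and the last paragraph of 9.6 all favour the change reading.

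**Conclusion.** The concern holds. The 24 per arm is right for a t-test on post-treatment PRWE with SD 18 and everyone analysed, but it does not establish the power of the comparison the plan names. With 24 per arm and both SDs 18, that power runs from 67% at r = 0.3 to 99% at r = 0.8. A pre-operative SD of 22 takes it down to 57% at r = 0.3. Exclusions can only reduce the analysed number from 24.

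At SD 18 and 24 per arm, ANCOVA stays at about 80% or more for any r (79.8% at r = 0). With equal SDs it gains about 17 points over the change score at r = 0.3 and 9 points at r = 0.5, and almost nothing at r = 0.8. The correlations, the pre-operative SDs and the 20 per arm are assumptions. Confidence is medium, because the size depends on them and 9.5 is not fully explicit. This should be corrected, but it is a matter of precision and clear justification, not of bias in the named test.

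**What to change.** - **9.5:** replace the 2-sample t-test on change with ANCOVA of post-operative PRWE at a named visit on treatment arm and baseline PRWE, and do likewise for the other outcomes. Report the adjusted difference with its 95% confidence interval.
- **Alternative for 9.5, with 9.1:** use a repeated-measures mixed model over the four post-operative visits with baseline as covariate, and amend 9.1 to keep every randomised subject with any post-operative data. Without that amendment, the model does not recover subjects discontinued for missed visits.
- **9.6:** state that 80% assumes 24 analysed per arm on post-treatment PRWE with SD 18. Add power over a stated range of loss and SD, or under ANCOVA over a stated range of correlation.

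The cost is one degree of freedom, wording in 9.5 and 9.6 (and in 9.1 if the mixed model is chosen), and a less favourable stated unadjusted power, for example 73% with 20 per arm. If r is near 0, ANCOVA has about 1 point less power than the post-treatment t-test (79.8% against 80.7%). No extra subjects, visits or data are needed.

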## 9.7 INTERIM ANALYSES

Not applicable.

## 9.8 PROTOCOL DEVIATIONS

Protocol deviations may include:

- Deviations from the protocol, contrary to protocol specifications (i.e., deviations from the protocol, eligibility, visit windows, etc.).
- Deviations affecting the endpoint outcome not previously specified in the protocol (i.e., deviation that had not been previously considered in the protocol or eligibility criteria, however having a clear impact on the primary outcome measure)

All protocol deviations will be reviewed and categorized as major (i.e., those that affect measurement or interpretation of the primary endpoint) or minor (those not affecting the primary endpoint).

